A DSMB (Data Safety Monitoring Board) will be set up headed by [name] MD, Duke Dept of Medicine, who has no relationship with this study. [name] is a renowned clinician who has been involved with several clinical trials, was the Division Chief of Rheumatology for many years in the Duke Department of Medicine. The DSMB will also include [name] [name] MD, of the Duke Dept of Anesthesiology, who is an experienced clinical trial physician and organizer, and a nationally renowned practitioner of pain medicine, in addition [name] PA-C, a very experienced provider in painful cranial neuropathies, of the Duke Dept of Neurosurgery.

The Data and Safety Monitoring Board (DSMB) serves as an independent group of experts that advises the team that runs this study. The members of the DSMB serve in an individual capacity and provide their expertise and recommendations. The primary responsibilities of the DSMB are to periodically review and evaluate the accumulated study data for participant safety, study conduct and progress, and advise on continuation of the trial. The DSMB considers study-specific data as well as relevant background knowledge about the pain condition, galcanezumab, and the specific patient population

under study. During the trial, the DSMB will review cumulative study data to evaluate safety, study conduct, and scientific validity and integrity of the trial. As part of this responsibility, DSMB members must be satisfied that the timeliness, completeness, and accuracy of the data submitted to them for review are sufficient for evaluation of the safety and welfare of study participants. The DSMB should also assess the performance of overall study operations and any other relevant issues, as necessary.

Items reviewed by the DSMB include:

- Interim/cumulative data for evidence of study-related adverse events;
- Data quality, completeness, and timeliness;
- Adequacy of compliance with goals for recruitment and retention;
- Adherence to the protocol;
- Factors that might affect the study outcome or compromise the confidentiality of the trial data,
- Factors external to the study such as scientific or therapeutic developments that may impact participant safety or the ethics of the study.

The DSMB should conclude each review with their recommendations to the Research Management Team (RMT). Recommendations regarding modification of the design and conduct of the study could include:

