- Modifications of the study protocol based upon the review of the safety data;
- Suspension or early termination of the study because of serious concerns about subjects' safety.

Confidentiality must always be maintained during all phases of DSMB review and deliberations. DSMB members must maintain strict confidentiality concerning all privileged study results provided to them.

DSMB membership reflects appropriately involved medical disciplines, also takes into account the pilot nature of our study.

No member of the DSMB has direct involvement in the conduct of the study. No member has financial, proprietary, professional, or other interests that may affect impartial, independent decision-making by the DSMB.

Meetings are set once a year and will be scheduled more frequently in case adverse effects occur more than 2x/ month of a severe AE per quarter.

The initial DSMB meeting should occur preferably before the start of the trial or as soon thereafter as possible. At this meeting the DSMB will discuss the protocol and its roll-out, mandatory triggers set for data review or analyses. Guidelines will address stopping the study for safety concerns.

Once a study is implemented, the DSMB will convene as often as necessary, but at least once annually, to examine the accumulated safety and enrollment data, review study progress, and discuss other factors (internal or external to the study) that might impact continuation of the study as designed. A DSMB meeting may be requested by DSMB members, the PI, the Duke University IRB, or study Principal Investigator at any time to

discuss safety concerns. Decisions to hold ad hoc meetings will be made by the PI and DSMB Chair. Meetings may be held by conference calls or videoconferences or as face-to-face meetings. In the event a DSMB member cannot attend a meeting, he/she may participate by conference call, in addition can provide written comments to the DSMB Chair for consideration at the meeting.

4) Necessary patient equipment/materials to generate data-points when home

Patients will be provided with a 200-page paper booklet.

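### On its plain reading, section 3 requires the PI's agreement for any ad hoc DSMB meeting, and it lets the first meeting, where review triggers are discussed, follow the start of dosing

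*Combined protocol and SAP*

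**What the plan says.** All the governing text is in section 3, Data Safety Monitoring Board, of the combined protocol and SAP.

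- **Status of the board.** It "serves as an independent group of experts that advises the team that runs this study". The section adds that no member has interests that could affect impartial decisions.
- **Who may ask for a meeting.** "A DSMB meeting may be requested by DSMB members, the PI, the Duke University IRB, or study Principal Investigator at any time".
- **Who decides.** "Decisions to hold ad hoc meetings will be made by the PI and DSMB Chair".
- **First meeting.** "The initial DSMB meeting should occur preferably before the start of the trial or as soon thereafter as possible". Its agenda follows: "At this meeting the DSMB will discuss the protocol and its roll-out, mandatory triggers set for data review or analyses". The next sentence reads: "Guidelines will address stopping the study for safety concerns". No such guidelines appear in the document.
- **Later meetings.** These are yearly, and "will be scheduled more frequently in case adverse effects occur more than 2x/ month of a severe AE per quarter". A further sentence has the board meet whenever needed and no less than yearly, without saying who judges the need.
- **Output.** The board makes recommendations to the Research Management Team, which under section 6 includes the PI.

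**The concern.** The purpose of an independent board is that someone other than the investigator can decide that the accumulating data need a look. Here the right to ask is wide, but the decision is given to two people, one of whom runs the trial. If they disagree, the text offers no way forward.

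Other parts of the protocol make this matter more. Treatment is open label, and under section 7 the PI gives the yes/no judgement on whether each event is related to treatment. The PI's side and the institution also act as sponsor, so no separate sponsor stands between the PI and the board. Section 7 sends SAE reports to the IRB and, on the IRB's decision, to the drug supplier. It does not name the DSMB in that chain, so meetings are the only review route the document describes for the board. Safety is the primary criterion of the study.

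The timing of the first meeting is a second, smaller matter. If it falls after dosing has begun, patients may be injected before the events that oblige the board to look at data have been settled.

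**Working it through.** The protocol gives no figure on this point to reproduce. The check is a comparison of passages, with a little timing arithmetic for context.

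**1. Request against decision.** The sentence on requests lists board members, the IRB and the PI (the PI twice, under two names). The sentence on decisions lists the PI and the Chair. The IRB and ordinary board members are in the first list but not the second, so they can ask but not decide. Nothing elsewhere in section 3 gives the Chair power to act alone on an ad hoc meeting.

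**2. Joint or either.** Two people joined by *and* as makers of a decision are most naturally read as deciding together. On that reading the PI's agreement is necessary. An either-one reading is possible, but the text does not state it.

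**3. Decision against independence.** A board described as independent of the team it advises sits uneasily with a rule under which the head of that team shares the decision on whether it meets. The two statements need to be reconciled.

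**4. Other routes to a meeting.** There are two.

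- The adverse-event trigger mixes a monthly and a quarterly count and cannot be applied as written.
- The promise to meet as needed names no one to judge the need.

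Neither mentions PI consent. Equally, neither says that the board may convene without the PI.

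**5. First meeting against first injection.** The Study Design / Overview section gives each patient 4 weeks of observation before treatment. A first meeting held shortly after the start could therefore still precede all dosing, but nothing requires it to. The review triggers are tied to that meeting by the text. The stopping guidelines are promised in the adjacent sentence and are not expressly tied to it.

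**6. Why the ad hoc route matters (context only).** Inputs from Study Design / Overview: three doses 4 weeks apart and 12 weeks of treatment. Sections 7 and 11 speak of 90 days. Assume exactly one scheduled meeting a year and patient start dates spread evenly over the year.

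- First to last injection: 2 × 28 = 56 days, and 56/365 = 15%.
- Treatment period: 12 × 7 = 84 days, and 84/365 = 23%; with 90 days, 90/365 = 25%.

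So 75% to 77% of patients would finish treatment with no scheduled meeting in that period. Review during dosing would then depend mainly on ad hoc and triggered meetings. These percentages describe the yearly interval. They do not measure the harm from shared control over ad hoc meetings, and the fix below would leave them unchanged.

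**The case against.** The strongest reply is that the board is only one of several safeguards. Section 7 requires the IRB to be told of any SAE within 24 hours, whatever the PI thinks of relatedness. It also asks investigators to alert the IRB to anything unusual. The IRB's safety commission has 48 hours to decide whether each SAE goes to the drug supplier at once. In addition, section 3 has the board meet more often on an adverse-event trigger and whenever needed. The sentence on requests names the PI twice, which suggests loose drafting rather than a deliberate blocking power. The 4-week observation period leaves room for a timely first meeting. And this is an open-label pilot of 20 patients.

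Much of this stands, and it rules out stronger readings that a reader might infer.

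- *That there is no independent check between annual meetings.* The IRB route contradicts this.
- *That the protocol gives the PI an express veto.* A need for the PI's agreement is the plain reading, but no sentence says that the PI may refuse.
- *That the ad hoc rule leaves the board unable to act on its own.* The board is advisory in any case and would remain so if the Chair could convene it. The defect lies in convening, not in acting.
- *That the harm can be sized by counting injections given before the first annual meeting.* Such a count needs an accrual period that the documents do not give, assumes no triggered or ad hoc meeting, and would be the same after the fix.

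What the reply does not do is give the board a clear way to meet without the PI. The IRB itself may only request a DSMB meeting, and review of the cumulative study data is assigned to the board.

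**Conclusion.** The point holds as a conflict within section 3: stated independence on one side, and a shared decision on ad hoc meetings with no tie-break on the other. It rests on reading the PI and Chair as deciding jointly. If either one alone was meant, the remedy is the same sentence, made explicit. The first-meeting limb holds more weakly. Dosing may begin before the review triggers are set, although the 4-week observation period makes that avoidable.

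No numerical size applies, and no estimate, test or sample-size statement is affected. The gain is in patient safety oversight, at almost no cost. Label: cheap improvement.

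**What to change.** Two changes in section 3.

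1. Replace the sentence on ad hoc decisions with one to this effect: *The DSMB Chair may convene an ad hoc meeting without the agreement of the PI; the PI may request a meeting but may not refuse one.* Board members and the IRB keep their right to request, and the Chair decides.
2. Require the initial meeting to take place before the first injection of the first patient, with the review triggers and the promised stopping guidelines adopted by then. Their content is for the board to settle and is not proposed here.

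The cost is possibly one or two extra short calls, which section 3 already allows by telephone or video, and a fixed date for the first meeting. No additional members, data or patients are needed.

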Before treatment, there will be a 4 week observation-only period, and another one 8 weeks post-treatment, so that the total study period will be 6 months.

We aim for 20 patients to be included in this study.

see more detailed graphics in the next section

In terms of ancillary, laboratory-based studies, we intend to draw blood before treatment and at the 45-, 75-, 105- and 135-day of treatment time-points. We will measure cytokine/chemokine/lipid pain- and inflammation markers in patients' serum, also determine microRNA in their serum, and genomic DNA polymorphisms, the latter only at baseline. Please see next section for more detail.

To establish safety of the anti-CGRP treatment in this patient cohort, blood draw at baseline and at the 45-, 75-, 105- and 135-days of treatment time-points will also include routine systemic sentinel/surveillance markers, namely comprehensive metabolic panel and complete blood count with differential, and complete urinalysis. No more than 45 ml of blood will be collected at any given visit.

In terms of additional safety parameters, we propose an open, patient-kept side-effect log, plus home-based recordings of blood pressure, heart rate and weight at a frequency of 2x/week.

We will set up a data and safety monitoring board for proper management and oversight of data handling and patient safety-related issue; see next section.

[figure not shown]
We expect to observe effective treatment, at least in a significant subgroup of patients. Effectiveness of treatment, also magnitude of any observed therapeutic effect will be correlated with the pain/inflammation proteinaceous, lipid and RNA-based biomarkers in patients' serum, also with any polymorphisms in the patients' genomic DNA.

We also expect galcanezumab treatment to show another record of safe treatment, our expectation sculpted by analysis of in-depth data from treatment of migraineurs. Yet we will remain vigilant and implement the proposed safety sentinel measures in order not to miss adverse effects. This appears prudent because trigeminal or glossopharyngeal nerve pain plus small-fiber neuropathy is a different underlying disorder than migraine, likely representing a higher prevalence in peri-menopausal female patients. We also believe it is likely that level of chronic pain suffering-associated stress will be higher in our study population than in migraineurs.

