[name] will be the Principal Investigator. He has the primary responsibility for ensuring the ethical conduct of this research study. This includes protecting human subjects' rights, safety and welfare, protocol compliance, and adherence to institutional, state and federal regulations and guidance, and for proper communication with the financial support source. He is responsible for ensuring informed consent is appropriately obtained from each participant and for appropriately maintaining study records. He is also responsible for complying with the financial and administrative policies and regulations associated with the award, overall fiscal management of the project, and conflict of interest disclosure. He will oversee all aspects of this trial, but some tasks can be delegated to other research team members. He will be responsible for ensuring that all research team members have appropriate education, training and qualifications to assume delegated study tests. All study team members are responsible for ensuring that the conduct of the study is compliant with institutional, state and federal regulations.

[name] and [name] will serve as sub-investigators.

Data entry and management will rely on a RedCap database that will be set up specifically for this study. The Research Coordinator/Research Nurse will be provided by Duke's Neurology Clinical Research Unit at [name].

7) Risks and Adverse Reactions – Adverse Event (AE) management

Investigators are responsible for monitoring the safety of subjects who have entered this study and for alerting the Duke University IRB to any event that seems unusual, even if this event may be considered an unanticipated benefit to the subject. The PI is responsible for the appropriate medical care of subjects during the study.

Investigators must document their review of each safety report.

The PI remains responsible for following, through an appropriate health care option, AEs that are serious or otherwise medically important, considered related to galcanezumab or the study, or that caused the patients to discontinue galcanezumab before completing the study. The patient should be followed until the event resolves, stabilizes with appropriate diagnostic evaluation, or is reasonably explained.

The frequency of follow-up evaluations of the AE is left to the discretion of the PI.

Lack of drug effect is not an AE.

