After the informed consent form (ICF) is signed, study site personnel will record via case report form (CRF) the occurrence and nature of each subject's preexisting conditions, including clinically significant signs and symptoms of the pain condition under treatment in this study. In addition, site personnel will record any new conditions as AEs. Investigators should record their assessment of the potential relatedness of each AE to galcanezumab and/or protocol procedure via CRF.

The PI will interpret and document whether or not an AE has a reasonable possibility of being related to galcanezumab, its injection, or a study procedure, taking into account the disease, co-morbid conditions, concomitant treatment or pathologies.

A “reasonable possibility” means that there is a cause and effect relationship between galcanezumab, and/or study procedure and the AE.

The PI answers “yes/no” when making this assessment.

Planned surgeries and nonsurgical interventions should not be reported as AEs unless the underlying medical condition has worsened during the course of the study.

If galcanezumab is discontinued for a given patient as a result of an AE, study site personnel must report this to the Duke IRB via CRF, clarifying if possible, the circumstances leading to discontinuations of treatment.

A severe AE (SAE) is any AE from this study that results in one of the following outcomes:

- death
- initial or prolonged inpatient hospitalization
- a life-threatening experience (that is, immediate risk of dying)
- persistent or significant disability/incapacity
- congenital anomaly/birth defect
- important medical events that may not be immediately life-threatening or result in death or hospitalization but may jeopardize the patient or may require intervention to prevent one of the other outcomes listed in the definition above. Examples of such medical events include allergic bronchospasm requiring intensive treatment in an emergency room or at home, blood dyscrasias or convulsions that do not result in inpatient hospitalization, or the development of drug dependency or drug abuse.

All AEs occurring after signing the ICF are recorded in the CRF and assessed for fulfilling criteria of SAE. SAE reports are forwarded to the Duke University IRB. For each SAE, the Duke University IRB safety commission will decide within 48h whether the case will be forwarded to Eli Lilly immediately.

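### The only general AE collection rule names new conditions, so worsening of a pre-existing condition, including the treated pain, has no clear route into the AE and SAE records

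*Combined protocol and SAP*

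**What the plan says.** All the relevant rules are in section 7 (Risks and Adverse Reactions) unless stated otherwise.

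- **Pre-existing conditions.** After consent, staff record on the CRF "the occurrence and nature of each subject's preexisting conditions, including clinically significant signs and symptoms of the pain condition under treatment in this study".
- **AE collection.** The next sentence reads: "In addition, site personnel will record any new conditions as AEs".
- **AE window.** "All AEs occurring after signing the ICF are recorded in the CRF and assessed for fulfilling criteria of SAE".
- **SAE definition.** "A severe AE (SAE) is any AE from this study that results in one of the following outcomes". The list that follows includes inpatient admission.
- **Planned procedures.** "Planned surgeries and nonsurgical interventions should not be reported as AEs unless the underlying medical condition has worsened during the course of the study".
- **Lack of effect.** "Lack of drug effect is not an AE".
- **Wider duties.** Investigators are responsible for "alerting the Duke University IRB to any event that seems unusual". In the Study Design overview, "we propose an open, patient-kept side-effect log, plus home-based recordings of blood pressure, heart rate and weight".

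No section gives a general definition of an AE. Section 7 says that pregnancy falls outside the AE definition, but the definition it refers to is not in the document. It also says that AE reporting follows that section, so staff have nowhere else to look. Under Primary Outcome Measures, safety is the primary criterion. It is stated as a safety profile, with no operational definition.

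**The concern.** A condition already on the pre-existing list is not new when it gets worse. Staff who follow the collection sentence as written have no instruction to record the worsening as an AE.

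The study population makes this matter. Every patient has trigeminal or glossopharyngeal pain plus painful small fiber neuropathy. Headache codes and fibromyalgia are allowed, patients may be up to 80 years old, and galcanezumab is added to all other therapy. In such patients, harm can plausibly appear as an existing problem getting worse. The overview itself asks for vigilance because this disorder differs from migraine.

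Omitting worsenings can only lower AE and SAE counts, which is the direction of the favorable result the trial hopes to show.

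**Working it through.** The plan gives no AE rate and no figure on this point, so there is nothing to reproduce. The check sets the rules side by side and follows six kinds of event through them.

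1. **New condition, no serious outcome.** It is an AE under the collection sentence.
2. **New condition leading to admission.** It is an AE, then an SAE by the listed outcome, and the 24-hour IRB notice applies.
3. **Listed condition worsens, and a planned procedure is involved.** The planned-procedure clause makes it reportable.
4. **Listed comorbidity worsens and leads to an unplanned admission.** It is not new, and the planned-procedure clause does not apply. The sentence on recording all AEs after consent helps only if the event already counts as an AE. There is no clear route.
5. **Treated pain worsens and leads to admission.** The pain is on the pre-existing list by explicit instruction. The lack-of-effect sentence may be read as excluding it, because it draws no line between non-response and deterioration. There is no clear route.
6. **Treated pain drifts up on the daily scale with no medical consequence.** It is captured as pain-outcome data, which is the right place for it.

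Cases 3 and 4 show the inconsistency: the same deterioration is reportable or not depending on whether a planned procedure is attached.

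**What depends on AE status.** In cases 4 and 5 the following steps are uncertain:

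- SAE classification, and with it the 24-hour IRB notice and the decision on forwarding to the drug supplier;
- the yes/no relatedness assessment and follow-up to resolution;
- the IRB report when galcanezumab is stopped because of an AE;
- the trigger for extra DSMB meetings, which section 3 ties to adverse effects and severe AEs.

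**Size.** Let w be the share of true AEs that are worsenings of a listed condition, and m the share of those that staff leave unrecorded.

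Proportional under-count of AEs = w × m

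If staff treat every worsening as an AE, m = 0 and the under-count is 0. If they follow the sentence literally and no other clause rescues the event, m = 1 and the under-count is w. The documents give neither w nor m, so the range runs from 0 to w and cannot be narrowed from them.

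For scale only: with 20 patients, one uncounted patient with an admission is the difference between 0/20 = 0% and 1/20 = 5%. That event is hypothetical.

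**The case against.** The strongest reply is that the text is incomplete rather than exclusionary, and much of this stands.

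- **Worsening is not barred.** A reader might infer that only new conditions are collected and that worsening is never an AE or SAE. The documents do not support that. The collection sentence contains no such restriction, and the planned-procedure clause makes some worsening reportable. It also suggests that the authors regard worsening as relevant.
- **Worse pain is recorded.** Patients rate pain and list medication daily (section 4), and section 11 compares treatment with run-in and with the post-treatment period. That is correct, but these data carry no seriousness or relatedness assessment. Section 11 also restricts the statistical analysis to completers, so a patient who worsens and withdraws drops out of that analysis too.
- **Other channels exist.** Home blood pressure, the open side-effect log, the instruction to contact the team about problems with galcanezumab, and the DSMB's review of cumulative data are not limited to new conditions. They help, but no rule turns a log entry or a home reading into an AE. The alert for unusual events is a matter of judgment, and worse pain in a chronic pain patient may not look unusual.
- **The primary safety outcome is undefined.** A reader might infer that worsenings are missing from it. That cannot be shown, because it is not defined as an AE count and section 11 specifies no AE-incidence analysis.
- **The CRF and SAE forms are not in the document.** They may handle worsening properly. The finding is about the protocol text.
- **Pain could be counted twice.** Making every rise above run-in an AE would duplicate the pain outcome as a safety event. This is a fair point, and the fix is limited accordingly.

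What remains is that the only general instruction omits worsening and that SAE status inherits the omission.

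**Conclusion.** The concern holds as an incomplete and internally inconsistent collection rule. A worsened pre-existing condition, including the treated pain, may be missed or recorded inconsistently as an AE or SAE even when it leads to admission. Any resulting bias in the AE and SAE record is downward. Its size cannot be derived from the documents.

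The conclusion rests on two assumptions: that staff follow section 7 as written, and that forms outside the document do not correct it. It does not depend on the sample size or on any event rate.

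The gap should be closed because safety is the primary criterion, and because onset, seriousness and relatedness may not be reliably recoverable if they are not recorded at the time.

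**What to change.** Make two changes in section 7 and carry them into the CRF guidance.

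1. **Collection sentence.** Replace it with: *site personnel will record as AEs any new condition and any clinically significant worsening in severity or frequency of a pre-existing condition compared with its state at consent or run-in.* This also brings the general rule into line with the planned-procedure clause.
2. **Lack-of-effect sentence.** State that lack of effect alone is not an AE, but that an event meeting a seriousness outcome, including one due to worsening of the treated pain, is recorded and assessed as an SAE. Add that ordinary fluctuation on the daily pain scale stays pain-outcome data.

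The cost is a somewhat higher AE count and a few more CRF lines, with no added visits or procedures. The change does not touch two separate rules that also limit the safety record: the end of active AE seeking after the 90-day treatment period, and the completers-only analysis in section 11.

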Study site personnel must alert the Duke IRB of any SAE within 24 hours of PI or any other member of the clinical team becoming aware of the event.

If alerts are issued via telephone, they are to be immediately followed with official notification on study-specific SAE forms. This 24-hour notification requirement refers to the initial SAE information and all follow-up SAE information.

Pregnancy does not meet the definition of an AE. However, to fulfill regulatory requirements any pregnancy should be reported following the SAE process to collect data on the outcome for both mother and fetus.

Investigators are not obligated to actively seek AEs or SAEs in subjects once they have completed the 90-day treatment period. However, if the investigator learns of any SAE, including a death, during the 60 day observational period, the PI must promptly notify the Duke IRB. This will also apply to an SAE after finishing the study if the PI considers the event reasonably possibly related to treatment with galcanezumab or study participation.

Suspected unexpected serious adverse reactions (SUSARs) are serious events that the investigator identifies as related to galcanezumab or procedure. United States 21 CFR 312.32 and European Union Clinical Trial Directive 2001/20/EC and the associated detailed guidances or national regulatory requirements in participating countries require the reporting of SUSARs. The Duke IRB has procedures that will be followed for the identification, recording and expedited reporting of SUSARs that are consistent with

global regulations and the associated detailed guidances.

Enrolled patients will be instructed to contact the PI and his study team as soon as possible if the patient has a complaint or problem with galcanezumab so that the situation can be assessed.

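### Section 7 defines a reasonable possibility of relatedness as actual causation, contradicting the possibility standard used elsewhere in the section; read literally, this could narrow SUSAR classification and adverse-event follow-up

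*Combined protocol and SAP*

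**What the plan says.** Section 7 (Risks and Adverse Reactions – Adverse Event management) sets the causality assessment in three consecutive steps. The PI is to document "whether or not an AE has a reasonable possibility of being related to galcanezumab, its injection, or a study procedure". The next sentence says that a reasonable possibility "means that there is a cause and effect relationship between galcanezumab, and/or study procedure and the AE". The response scale follows: "The PI answers “yes/no” when making this assessment".

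The same section describes the judgement differently elsewhere. Shortly before, it says: "Investigators should record their assessment of the potential relatedness of each AE to galcanezumab and/or protocol procedure via CRF". For SAEs arising after the study is finished, notification applies "if the PI considers the event reasonably possibly related to treatment with galcanezumab or study participation". SUSARs, whose name begins with the word suspected, "are serious events that the investigator identifies as related to galcanezumab or procedure".

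Relatedness is also one of the listed grounds for following an adverse event. The other grounds are that it is serious, is otherwise medically important, or caused the patient to stop galcanezumab.

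**The concern.** The question and its definition set different thresholds. An event that galcanezumab might have caused, but for which causation is not established, meets the question as asked and fails the definition. The scale is binary, so there is no intermediate category for it.

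Such events are likely to be the hard cases here. Treatment is open label with no control arm described. Galcanezumab is added to all existing therapy, and the PI must weigh co-morbid conditions and concomitant treatment. In that setting, causation is difficult to assert for an individual patient. Safety is the primary criterion, and the Overview asks for vigilance because the underlying disorder differs from migraine. A definition that may push uncertain events to a negative answer works against that aim.

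**Working it through.** No arithmetic in the plan bears on this point and there is no stated figure to reproduce. The check sets the wordings side by side, then traces one event through every route that could use the causality answer.

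**Step 1: the standards in section 7.**

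| Place in section 7 | Wording | Threshold |
|---|---|---|
| Recording on the CRF | "Investigators should record their assessment of the potential relatedness of each AE to galcanezumab and/or protocol procedure via CRF" | possibility |
| PI's question | "whether or not an AE has a reasonable possibility of being related to galcanezumab, its injection, or a study procedure" | possibility |
| Definition of the term in that question | "means that there is a cause and effect relationship between galcanezumab, and/or study procedure and the AE" | causation present |
| SUSARs | "serious events that the investigator identifies as related to galcanezumab or procedure" | relatedness, threshold not restated |
| SAEs after study end | "if the PI considers the event reasonably possibly related to treatment with galcanezumab or study participation" | possibility |

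Only the definition sets the threshold at causation. Nothing says which wording governs the yes/no item.

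**Step 2: trace an event that is possibly but not demonstrably drug-related, answered no under the literal definition.**

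- CRF record: kept. All adverse events after consent are recorded.
- SAE notice to the IRB during the study: kept. Any SAE must be notified within 24 hours, whatever its cause. An SAE that the investigator learns of in the 60-day observation period must also be notified promptly, without a relatedness condition.
- SUSAR status: lost on the literal text, because the definition requires the investigator to identify the event as related. The IRB's own SUSAR procedures might still catch it, but they are not described.
- Follow-up under section 7: kept if the event is serious, medically important or led to discontinuation. Otherwise relatedness is the only listed ground, and it is lost.
- SAE after study end: notification depends on its own possibility wording. It is lost only if the strict definition is read into that wording.
- DSMB review: not shown to be lost. Section 3 gives the board cumulative study data and accumulated safety data, with no filter by PI attribution.

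**Step 3: direction and size.** Let E be the number of events with causation judged present and P the number judged only possible. The strict definition classes E events as related; the possibility standard classes E + P. The difference is (E + P) − E = P, which is zero or more, so the strict definition can never give a higher count. The share of related events missed is P/(E + P). This is 0 if no event is merely possible and 1 if every such event is. The documents give neither E nor P, so nothing narrower can be derived.

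**The case against.** The strongest reply is that one loosely worded sentence will not govern practice. The PI's question and the CRF instruction are both framed as possibility, so a PI could answer yes for a possible reaction. That stands to this extent: miscoding is a risk under a literal reading, not a certain outcome. It does not remove the conflict, because a single yes/no item is left with two thresholds.

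A second reply is that other safeguards protect patients. All events are recorded, any SAE reaches the IRB within 24 hours, and the IRB decides within 48 hours whether to forward an SAE to the company immediately. Unusual events and discontinuations due to adverse events are also reported to the IRB. These provisions reduce the harm. They do not correct the recorded causality or restore the follow-up ground for lesser events.

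Three stronger readings are tempting and are not supported:

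- *Possible reactions drop out of DSMB review.* A reader might infer this from the listed item "Interim/cumulative data for evidence of study-related adverse events". That item says what the board looks for in the data. It does not restrict what the board receives, and the trigger for extra meetings names no relatedness condition.
- *The primary safety outcome is biased.* No section makes a count of related events the endpoint, and the Brief Statistical Analysis Plan specifies none. Laboratory panels, urinalysis, the patient side-effect log and home measurements do not depend on attribution.
- *Notification after study end necessarily depends on the yes/no item.* That rule states its own test and does not refer to the CRF item. The most that can be said is that the defined term might be carried over.

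**Conclusion.** The inconsistency is real and visible on the page. Within section 7, a term of possibility is defined as causation, against the wording before and after it. If the definition is followed literally, an event that is only possibly due to galcanezumab may be coded unrelated. Three consequences could follow:

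- a serious event falls outside the SUSAR definition;
- an event that is not serious, not medically important and did not lead to discontinuation loses its follow-up trigger;
- if the definition carries over, SAE notification after study end is narrowed.

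The conclusion assumes that the PI applies the sentence as written and, for SUSARs, that the undescribed IRB procedures do not compensate. The size is unknown; only the direction is fixed. Correction is worthwhile because safety is the primary criterion and no comparator is described against which attribution could be checked. This is a wording defect with a reporting consequence. It is not evidence that events would go unrecorded or be withheld from the DSMB.

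**What to change.** Reword the defining sentence in section 7 so that a reasonable possibility means that a cause-and-effect relationship between the event and galcanezumab or a study procedure *may reasonably exist*. State that this one standard applies to the yes/no causality item on the CRF, to SUSAR classification, to the relatedness ground for adverse-event follow-up, and to SAEs after study end. A wider phrase, such as one covering any event for which a link cannot be excluded, is not needed to remove the contradiction.

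The cost is one sentence plus a cross-reference at each of those places, with the CRF completion instructions aligned. No analysis or sample size changes. The downside is that somewhat more events may be classed as related, with a corresponding increase in reporting and follow-up work.
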